## STATEMENT OF COMPLIANCE

(1) [The trial will be carried out in accordance with International Council on Harmonisation Good Clinical Practice (ICH GCP) and the following:

- United States (US) Code of Federal Regulations (CFR) applicable to clinical studies (45 CFR Part 46, 21 CFR Part 50, 21 CFR Part 56, 21 CFR Part 312, and/or 21 CFR Part 812).

National Institutes of Health (NIH)-funded investigators and clinical trial site staff who are responsible for the conduct, management, or oversight of NIH-funded clinical trials have completed Human Subjects Protection and ICH GCP Training.

The protocol, informed consent form(s), recruitment materials, and all participant materials will be submitted to the IRB for review and approval. Approval of both the protocol and the consent form(s) must be obtained before any participant is consented. Any amendment to the protocol will require review and approval by the IRB before the changes are implemented to the study. All changes to the consent form(s) will be IRB approved; a determination will be made regarding whether a new consent needs to be obtained from participants who provided consent, using a previously approved consent form.]

## 1 PROTOCOL SUMMARY

*No text is to be entered in this section; rather it should be included under the relevant subheadings below. It may be useful to complete this section after the relevant sections in the protocol have been completed.*

### 1.1 SYNOPSIS

Title:	Examining Flexibility in Attentional Control
Grant Number:	1R15EY030247
Study Description:	Examine task switching when participants receive a target color cue or distractor color cue, and meaning and/or color change across trials
Objectives :	Examine task switching
Endpoints :	Single day of testing
Study Population:	27, 15 F/ 11M, healthy adults, Lehigh University
Phase * or Stage:	NA
Description of Sites/Facilities Enrolling Participants:	Lehigh University
Description of Study Intervention/Experimental Manipulation:	participants receive a target color cue or distractor color cue, and meaning and/or color change across trials
Study Duration :	2 months
Participant Duration:	30 minutes

### 1.2 SCHEMA

### 1.3 SCHEDULE OF ACTIVITIES

	Pre-screening (Pre-consent)	Visit 1 Day 1
Participants only see experiment if meet criteria	X	
Informed Consent		X
Demographics		X
Outcome Evaluation		
Visual Search Performance		X
Randomization (Trial order)		X
Adverse Events Reporting		X

## 2 INTRODUCTION

### 2.1 STUDY RATIONALE

The PI provided the first evidence that attentional control can also be used to ignore known distractor features (Arita, [name], & Woodman, 2012). In this study, participants received a cue before each trial of a visual search task where they searched for a shape-defined target (a gap-up or gap-down Landolt-c) and reported the location of the gap. The cue could be a positive cue (indicating the target would appear in that color in the upcoming array), a negative cue (indicating the target *would not* appear in that color in the upcoming array), or a neutral cue (the cued color did not appear in the upcoming array). These cue meanings were manipulated across blocks. Importantly, because only two colors appeared in the search array, the positive and negative cues had the same information value. If participants used the cue, they could reduce the number of items they needed to search to find the target by half. We found participants can use visual attentional control to actively ignore items based on a feature cue, as indicated by reaction time (RT) benefits for the negative cued condition compared to the neutral condition.

In this study, participants will receive a cue on each trial that indicates a feature (e.g. red) and the cue meaning (positive + or negative -). Across trials, we will be able to independently alter the feature template and the cue meaning (Figure 5A). This will allow us to ensure the results are driven by shifts in the cue meaning, and not simply alterations to the color that is cued. This will lead to trials where both the feature and the meaning repeat (RE-repeat trials), trials where only the cue feature changes (CC-color change, meaning repeat), trials where only the cue meaning changes but the color repeats (MC-meaning change, color repeat), and trials where both feature and cue meaning change (BC-both change). To look for task switching costs, we will subtract the reaction times for repeat trials from each type of switch trials. Importantly, the visual search is defined by a shape-defined target across all trials, meaning that there should be no cross talk or response interference that could interfere with our ability to measure task-switching costs (Koch, Poljac, Müller, & Kiesel, 2018).

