## 3 OBJECTIVES AND ENDPOINTS

OBJECTIVES	ENDPOINTS	JUSTIFICATION FOR ENDPOINTS	PUTATIVE MECHANISMS OF ACTION

Primary
 
Compare Task-Switching Costs for Positive Target Cues and Negative Distractor Cues
	Reaction Time Accuracy	Cognitive Function	Conflict in Cognitive Control leads to task-switching costs

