## 6 STUDY INTERVENTION(S) OR EXPERIMENTAL MANIPULATION(S)

## 6.1 STUDY INTERVENTION(S) OR EXPERIMENTAL MANIPULATION(S) ADMINISTRATION

### 6.1.1 STUDY INTERVENTION OR EXPERIMENTAL MANIPULATION DESCRIPTION

Participants will receive one of three types of visual cues before performing a visual search task. Positive cues for visual search (cues to enhance), or negative cues for visual search (cues to suppress). After subjects receive the color cue for a trial, they will perform a visual search task for a shape-defined target (landolt-C). We will examine task switching costs for changes in the color of the cue, changes in the meaning of the cue, neither or both. We will measure 'task-switching costs' by contrasting reaction times when an aspect of the trial changes compared to when neither aspect of the trial changes compared to the previous trials. We will collect behavioral results using Matlab and a computer.

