## 2 STATISTICAL CONSIDERATIONS

### 2.1 STATISTICAL HYPOTHESES

If the negative template requires the general inhibition of the oculomotor system to reduce the likelihood of the prepotent response, we expect to find a unidirectional switch cost (e.g. a switch cost for positive cues which is not present for negative cues).

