#### 2.4.2 ANALYSIS OF THE PRIMARY ENDPOINT(S)

For both Reaction time and Accuracy, we will perform an ANOVA with these factors: Cue Meaning (Target Color Positive Cue or Distractor Color Negative Cue) x Cue Meaning Repetition (Repeat, Non-Repeat) X Cue Color Repetition (Repeat, Non-Repeat) Repetition.

---

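### The stated meaning-change minus repeat cost also contains any effect of a change in target colour; define the meaning-switch cost within each cue type by a contrast already in the planned ANOVA, and name the term that tests the hypothesis

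*Combined protocol and SAP*

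**What the plan says.** Section 3 gives one objective: "Compare Task-Switching Costs for Positive Target Cues and Negative Distractor Cues". The cost is described in two places. Section 2.1 (Study Rationale) defines four trial types: RE (colour and meaning repeat), CC (only the cued colour changes), MC (only the meaning changes) and BC (both change). It then says "we will subtract the reaction times for repeat trials from each type of switch trials". Section 6.1.1 describes the cost in the same way, as "contrasting reaction times when an aspect of the trial changes compared to when neither aspect of the trial changes". Section 2.1 also says the design will "ensure the results are driven by shifts in the cue meaning, and not simply alterations to the color that is cued". It does not mention repetition of the target's colour.

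The hypothesis in section 2.1 (Statistical Hypotheses) is "a switch cost for positive cues which is not present for negative cues". Section 2.4.2 says "For both Reaction time and Accuracy, we will perform an ANOVA with these factors": Cue Meaning ("Target Color Positive Cue or Distractor Color Negative Cue"), Cue Meaning Repetition and Cue Color Repetition. It does not identify one term as the switch cost or as the test of the hypothesis.

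**The concern.** A positive cue gives the target's colour; a negative cue gives a colour the target will not have. If the cued colour stays the same and the meaning flips, the target must move into or out of that colour. Every MC trial is therefore also a target-colour-change trial. On positive RE trials the target colour cannot change. If responses are slower, or less accurate, when the target's colour differs from the previous trial, positive MC-RE will show a cost even if switching meaning costs nothing. Independent manipulation of cued colour and meaning does not remove this, because it controls the cued colour and not the target's colour.

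At stake is how each cost is read. A colour-repetition effect could be reported as a meaning-switch cost for positive cues, or could produce an apparent cost for negative cues and so obscure the predicted absence of one.

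**Working it through.** **Inputs.** From the documents: the cue and trial-type definitions (section 2.1, Study Rationale); n=24, alpha 0.05, eight measurements, correlation 0.5 and f=0.2 (section 2.2, Sample Size Determination). Assumed: two colours per array, since "only two colors appeared in the search array" describes the earlier study; two cue types, since section 6.1.1 mentions three but describes two; balanced cells; an additive effect B of a target-colour change. K, the colour pairing and B are not in the available text (Figure 5A is not shown), so ranges are used.

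**The plan's own figure.** Noncentrality = 0.2² x 24 x 8 / (1 - 0.5) = 15.36, with 7 and 161 df and critical F 2.067, gives power 0.8116. This reproduces the plan. It is a 7-df calculation, not one for a switch-cost contrast.

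**Probability that the target colour changes**, when the second array colour is drawn freely from the other K-1:

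| Cue | RE | CC | MC | BC |
|---|---|---|---|---|
| Positive | 0 | 1 | 1 | (K-2)/(K-1) |
| Negative | (K-2)/(K-1) | 1-(K-2)/(K-1)² | 1 | (K-2)/(K-1) |

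**Share of B in each cost**, putting these probabilities into the contrasts:

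- MC-RE: positive 1 - 0 = 1 for every K; negative 1 - (K-2)/(K-1) = 1/(K-1).
- Averaged contrast [(MC+BC)-(RE+CC)]/2: positive (K-2)/[2(K-1)]; negative (K-2)/[2(K-1)²].

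| K (free pairing) | MC-RE, pos / neg | Averaged, pos / neg | Pos minus neg: MC-RE | Pos minus neg: averaged |
|---|---|---|---|---|
| 2 | 1 / 1 | 0 / 0 | 0 | 0 |
| 3 | 1 / 1/2 | 1/4 / 1/8 | 1/2 | 1/8 |
| 4 | 1 / 1/3 | 1/3 / 1/9 | 2/3 | 2/9 |
| 6 | 1 / 1/5 | 2/5 / 2/25 | 4/5 | 8/25 |

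The last column is the share in Cue Meaning x Cue Meaning Repetition. With fixed colour pairs at K=4, MC-RE carries 1 / 1 and the averaged contrast 1/3 / 1/3, so with equal B both positive-minus-negative differences carry none.

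**Where B goes at K=2.** The change probabilities are RE 0, CC 1, MC 1, BC 0 for both cue types. This is exactly the Meaning Repetition x Color Repetition pattern: (BC-CC)-(MC-RE) = (0-1)-(1-0) = -2. That interaction is completely aliased with target-colour repetition.

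**Exact cue repetition.** RE is the only cell in which the identical cue recurs. Any such benefit enters MC-RE in full and the averaged contrast by half.

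**Precision.** In units of the between-participant SD of one cell mean, at correlation 0.5:

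- MC-RE: SD = √(2 x 0.5) = 1.00.
- Averaged contrast: SD = √(4 x 1/4 x 0.5) = 0.71.
- Interaction (difference of two averaged contrasts): SD = √(8 x 1/4 x 0.5) = 1.00.

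Two-sided t test, 23 df: a cost of 0.4 present in both MC and BC is detected with 47% power by MC-RE (noncentrality 0.4 x √24 / 1.00 = 1.96) and 76% by the averaged contrast (0.4 x √24 / 0.707 = 2.77). The interaction reaches 80% for a positive-only cost of 0.6 (0.6 x √24 / 1.00 = 2.94).

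**Chance of p<.05 for positive cues with no meaning-switch cost**, B assumed:

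| B (cell SD) | MC-RE, any K | Averaged, K=2 | Averaged, K=4 free |
|---|---|---|---|
| 0.1 | 8% | 5% | 6% |
| 0.2 | 16% | 5% | 7% |
| 0.4 | 47% | 5% | 14% |

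B=0.4 is a large assumption: at K=2 it puts four cells at +0.2 and four at -0.2, which alone is f=0.20, the whole planned effect.

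**The case against.** The strongest reply is that the only planned inference is the ANOVA. It already contains Cue Meaning x Cue Meaning Repetition, the natural test of the hypothesis, and no section plans a separate test of MC-RE. That stands, and it is why this is a wording point.

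A reader might infer that the description of the cost contradicts the ANOVA. It does not. The rationale subtracts RE from all three change types, and the averaged contrast is a combination of those subtractions: [(MC-RE)+(BC-RE)-(CC-RE)]/2. What is missing is a statement that this combination, and not MC-RE alone, is the meaning-switch cost.

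A reader might also infer that the trial is biased toward its prediction. The documents do not support that. No size for B is given. With equal B, the positive-minus-negative comparison carries none of it at K=2 or with fixed pairs, even from MC-RE. A bias toward the prediction arises only with K above 2, free pairing and slowing after a target-colour change, and the available text does not establish those conditions.

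**Conclusion.** The point holds as a minor to moderate problem of definition. That positive MC-RE contains all of B follows from the cue definitions alone. The negative-cue shares rest on two colours per array, two cue types and the stated pairing. Where B is the same for both cue types and K=2, the damage is to the size of each cost and to the conclusion that negative cues show none, not to the comparison between cue types.

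Two further inferences go too far. One is that the ANOVA removes the problem: cancellation is exact only at K=2 with additive effects and balanced cells, and with free pairing the positive-cue averaged contrast keeps 1/4, 1/3 and 2/5 of B at K=3, 4 and 6. The other is that the Meaning Repetition main effect is enough: it averages over positive and negative cues, so it cannot test a cost for one and not the other. The rejection rates above illustrate assumed values of B; they do not estimate this trial's error rate.

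**What to change.** - Sections 2.1 (Study Rationale) and 6.1.1: define the meaning-switch cost as [(MC+BC)-(RE+CC)]/2 within each cue type. State that MC-RE alone will not be read as a meaning-switch cost.
- Section 2.4.2: name Cue Meaning x Cue Meaning Repetition, followed by the Meaning Repetition effect within each cue type, as the test of the hypothesis in section 2.1 (Statistical Hypotheses).
- Section 2.4.2: state that Meaning Repetition x Color Repetition will not be interpreted as a pure cue-level interaction, because at K=2 it is aliased with target-colour repetition.
- State the number of colours and how they are paired. If K exceeds 2, say that some of B remains. A trial-level analysis adjusting for target-colour repetition is then an optional sensitivity analysis, if the trial files record target colour.

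The cost is wording; the ANOVA is unchanged. There are two downsides. The cost now averages over colour-repeat and colour-change trials, so a meaning-switch cost confined to one of them is diluted. And the named interaction has 80% power at n=24 only for a positive-only cost of about 0.6 cell SD, although that limit already applies to this term in the planned ANOVA.

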### 2.2 BACKGROUND

Previous research has shown that, when there are no competing task demands, attention is likely to be directed to items in the visual field that match working memory (Downing, 2000). This suggests that the prepotent response is to attend to memory-matching items, whereas to utilize a negative cue one must actively avoid attending the memory-matching items. This is a good example of how higher-order cognitive control can be used to inhibit prepotent responses. A similar example from oculomotor control is the anti-saccade task. In this task, participants must either make a pro-saccade toward a cue or an anti-saccade away from the cue, depending on the identity of the cue. A unidirectional switch cost has been shown within the anti-saccade task when participants must engage in task switching between pro- and

anti-saccades (Weiler & Heath, 2012). When participants switch from an anti-saccade task to a pro-saccade task, there is a typical switch cost as compared to pro-saccade repetition. However, the opposite pattern is found for anti-saccades- participants are either faster to perform an anti-saccade after a prosaccade (task switch) compared to an anti-saccade repetition (Barton, et. al, 2002) or show no task switch effect (Weiler & Heath, 2012). This is thought to reflect a residual inhibition of the pre-potent response following an anti-saccade. This slows a subsequent pro-saccade, but can also slow an anti-saccade as well. Therefore, the unidirectional switch cost is a hallmark of inhibition within the oculomotor system.

## 2.3 RISK/BENEFIT ASSESSMENT

*The following subsections should include a discussion of known risks and benefits, if any, to human participants. Text from the corresponding sections of the Human Subjects section of the grant application, and/or IRB package may be used here.*

### 2.3.1 KNOWN POTENTIAL RISKS

The risks associated with the behavioral tasks are similar to working on a computer or playing a video game. They include possible eye strain, and boredom. We will try to reduce the possibility of these risks by providing frequent breaks during the experiment (approximately every 5 minutes during data recording).

### 2.3.2 KNOWN POTENTIAL BENEFITS

There are no direct benefits expected for the participants, and no clinical benefits, however many participants enjoy being able to learn more about how we use behavioral responses to understand more about cognition.

The cognitive processes subserving attention and memory are critical for daily functioning. Individuals who have deficits in these cognitive processes, such as individuals with Schizophrenia, often have difficulty in succeeding in their pursuits. Learning more about how these processes occur in typical adults may lead to insights into how to help individuals with cognitive deficits, or improve these functions in typical adults.

### 2.3.3 ASSESSMENT OF POTENTIAL RISKS AND BENEFITS

The risks associated with the behavioral tasks are similar to working on a computer or playing a video game, and the benefits for our understanding of basic human cognition are present. Therefore, we think the benefits outweigh the risks.

## 3 OBJECTIVES AND ENDPOINTS

OBJECTIVES	ENDPOINTS	JUSTIFICATION FOR ENDPOINTS	PUTATIVE MECHANISMS OF ACTION

Primary
 
Compare Task-Switching Costs for Positive Target Cues and Negative Distractor Cues
	Reaction Time Accuracy	Cognitive Function	Conflict in Cognitive Control leads to task-switching costs

## 4 STUDY DESIGN

*No text is to be entered in this section; rather it should be included under the relevant subheadings below.*

### 4.1 OVERALL DESIGN

Hypothesis: If the negative template requires the general inhibition of the oculomotor system to reduce the likelihood of the prepotent response, we expect to find a unidirectional switch cost. Within-Subjects, single arm design, single site.

Visual Search Information Type (target or distractor information) Participants will have information about targets or distractors via cues before a visual search trials, in different trials of the intervention.

### 4.2 SCIENTIFIC RATIONALE FOR STUDY DESIGN

*Within-subjects design lead to strong conclusions about cognitive function.*

### 4.3 JUSTIFICATION FOR INTERVENTION

*Typical duration of trials, 481, for behavioral studies.*

### 4.4 END-OF-STUDY DEFINITION

*Complete 481 trials in single day.*

## 5 STUDY POPULATION

## 5.1 INCLUSION CRITERIA

In order to be eligible to participate in this study, an individual must meet all of the following criteria:

1. Provision of signed and dated informed consent form
2. Normal or corrected-to-normal visual acuity
3. Normal color vision
4.  $\geq 18$  years of age

## 5.2 EXCLUSION CRITERIA

## 5.3 LIFESTYLE CONSIDERATIONS

N/A

## 5.4 SCREEN FAILURES

N/A

## 5.5 STRATEGIES FOR RECRUITMENT AND RETENTION

We plan to include women and minorities in this study. Participants will be recruited from the Lehigh University community. As such, we expect the ethnicity distribution of our sample to roughly match the ethnicity distribution of Lehigh (see Figure 1). Lehigh's student body is 55% male and 45% female, so we also expect this to be represented in our sample. We will gather information on participant age, sex, and ethnicity for reporting purposes, and these factors will be entered into analysis as covariates in our statistical analyses. We have no a priori expectations of differences based on these factors from prior research, but will include these factors in our analysis to ensure that previous research has not neglected between group differences.

**Rationale for selection:** Our research is designed to assess basic research related to human visual attentional control. As such, we assume the basic processes will be shared among most adults humans. We will take a convenience sample of adults to learn more about these basic procedures.

**Outreach programs:** Participants will be recruited from low-level Psychology participant pools, which are often taken as a general education requirement at Lehigh. Paid participants will be recruited via fliers and the Lehigh Paid Participant Pool. Fliers are posted around Lehigh's campus as well as in public locations within the community (grocery stores, other higher education institutions, coffee shops, etc.). Most paid participants come from the Lehigh community, so we expect the sampling to draw heavily from Lehigh.

## 6 STUDY INTERVENTION(S) OR EXPERIMENTAL MANIPULATION(S)

## 6.1 STUDY INTERVENTION(S) OR EXPERIMENTAL MANIPULATION(S) ADMINISTRATION

### 6.1.1 STUDY INTERVENTION OR EXPERIMENTAL MANIPULATION DESCRIPTION

Participants will receive one of three types of visual cues before performing a visual search task. Positive cues for visual search (cues to enhance), or negative cues for visual search (cues to suppress). After subjects receive the color cue for a trial, they will perform a visual search task for a shape-defined target (landolt-C). We will examine task switching costs for changes in the color of the cue, changes in the meaning of the cue, neither or both. We will measure 'task-switching costs' by contrasting reaction times when an aspect of the trial changes compared to when neither aspect of the trial changes compared to the previous trials. We will collect behavioral results using Matlab and a computer.

### 6.1.2 ADMINISTRATION AND/OR DOSING

*Single day of testing, all conditions occur within single block of testing behavior.*

## 6.2 FIDELITY

### 6.2.1 INTERVENTIONIST TRAINING AND TRACKING

*Participants are all read the same instructions before trials begin to ensure understanding.*

## 6.3 MEASURES TO MINIMIZE BIAS: RANDOMIZATION AND BLINDING

*Within-subjects manipulation, no blinding.*

## 6.4 STUDY INTERVENTION/EXPERIMENTAL MANIPULATION ADHERENCE

*Practice trials were administered to ensure participants understood the task instructions.*

## 6.5 CONCOMITANT THERAPY

*N/A*

### 6.5.1 RESCUE THERAPY

*N/A*

## 7 STUDY INTERVENTION/EXPERIMENTAL MANIPULATION DISCONTINUATION AND PARTICIPANT DISCONTINUATION/WITHDRAWAL

### 7.1 DISCONTINUATION OF STUDY INTERVENTION/EXPERIMENTAL MANIPULATION

*Participants are informed their participation is voluntary, and they may stop participating at any time during the 30-minute testing session.*

